To assess the diagnostic performance of a rapid ultrafiltration test (without distinguishing between 15- and 30-minute trials) in detecting preload dependence in critically ill patients treated with continuous renal replacement therapy, by quantifying the change in cardiac index induced by the test and comparing it to that induced by a postural maneuver (reference standard) performed after the ultrafiltration test.

Secondary Objectives

- To assess the diagnostic performance of the 15-minute and 30-minute rapid ultrafiltration tests, respectively, using the same methodology.
- To determine the optimal threshold of cardiac index variation that defines preload dependence for each test (pooled and separately), with calculation of sensitivity, specificity, positive and negative predictive values.
- To compare the diagnostic performance of ultrafiltration tests (pooled and separate) with that of the pre-test postural maneuver.
- To compare the diagnostic performance between the 15-minute and 30-minute tests.
- To evaluate the impact of ultrafiltration tests on additional hemodynamic variables (absolute values and relative changes from baseline): central venous pressure, heart rate, mean and pulse arterial pressure, extravascular lung

water, pulmonary vascular permeability index, and global end-diastolic volume index.

- To assess the ability of ultrafiltration tests (pooled and separate) to predict hemodynamic instability with preload dependence occurring within 8 hours following the test.

Methodology / Study Design

- Pilot study
- Physiological, prospective, single-center, open-label
- Sequential crossover design with sealed-envelope randomization of intervention order
- Diagnostic test evaluation (rapid ultrafiltration challenge)

Primary Endpoint

Diagnostic performance of a rapid ultrafiltration test (regardless of duration), assessed by the area under the ROC curve (receiver operating characteristics) of cardiac index variation compared to the reference measurement (postural maneuver performed after the test).

Secondary Endpoints

- Diagnostic performance of the 15-minute and 30-minute rapid ultrafiltration tests, assessed by ROC analysis of cardiac index variation and comparison with the reference maneuver.
- Optimal thresholds (and 95% CI) of cardiac index variation for each test, determined using the Youden index, with associated sensitivity, specificity, PPV, and NPV.

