Diagnostic accuracy will be assessed by the change in calibrated cardiac index induced by the ultrafiltration challenge compared with the reference postural maneuver (passive leg raise or Trendelenburg) performed *after* the challenge.

Secondary Objectives

1. To evaluate separately the diagnostic performance of the 15-minute and 30-minute UF challenges.
2. To determine the optimal threshold of calibrated cardiac index variation defining preload dependence for each test (pooled and separate), with sensitivity, specificity, PPV, and NPV.
3. To compare diagnostic performance of UF challenges (pooled and separate) with that of the pre-test postural maneuver.
4. To compare diagnostic performance between the 15-minute and the 30-minute challenges.
5. To assess the effect of ultrafiltration challenges on other hemodynamic parameters (absolute values and relative changes from baseline): central venous pressure (CVP), heart rate (HR), mean arterial pressure (MAP), pulse pressure, extravascular lung water (EVLW), pulmonary vascular permeability index (PVPI) and global end-diastolic volume index (GEDVi)
6. To evaluate the ability of ultrafiltration challenges to predict hemodynamic instability with preload dependence within 8 hours after the test.

STUDY DESIGN / METHODOLOGY

Type of Research

- Pilot study
- Physiological, prospective, single-center, open-label
- Sequential crossover design with randomization of challenges' order
- Diagnostic test evaluation

Study Population

Inclusion Criteria

- Adults ≥ 18 years hospitalized in the ICU
- Mechanical ventilation and sedation
- Acute kidney injury KDIGO stage 3
- CRRT initiated < 14 days before inclusion
- With a calibrated continuous cardiac index monitoring device in place (PiCCO®, Pulsion Medical, Feldkirch, Germany)

- Informed consent (patient or representative)

Exclusion Criteria

- Arterial lactate > 4 mmol/L
- Calibrated cardiac index < 2 or > 4 L/min/m²
- Preload dependence identified within the preceding 2 hours
- ECMO
- Acute hemorrhage
- End stage chronic kidney disease or renal graft recipient
- Acute stroke with coma
- Fulminant hepatitis
- Inability to perform PLR: amputation, inferior vena cava obstruction, abdominal compartment syndrome
- Pregnancy or breastfeeding
- Imminent death
- Decision of withholding of care
- Patients under legal protection (guardianship, trusteeship, detention)
- Already included in the study

Number of Patients

- 20 patients included

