4. Comparison of diagnostic performance between the 15-minute and 30-minute challenges ROC AUCs compared using DeLong's test.
5. Analysis of additional hemodynamic parameters: CVP, HR, MAP, Pulse pressure, EVLW, PVPI and GEDVi (absolute values and relative changes, correlated with cardiac index variation).

6. Incidence of hemodynamic instability within 8 hours post-test (tachycardia, hypotension, decreased CI, mottling).

Study duration

- Inclusion period: 18 months
- Maximum participation per patient: 72 hours
- Total study duration: 18 months + 3 days

Sample size

- 20 patients planned.
- Each undergoes 2 ultrafiltration challenges (15- and 30-minute, randomized).
- Total: 40 evaluable ultrafiltration challenges.

The sample size was chosen pragmatically, consistent with the pilot/exploratory nature of the study.

STUDY PROCEDURES AND CONDUCT

Overall Study Flow

1. Screening and Inclusion
 - Verify inclusion and exclusion criteria.
 - Provide information to patient or legally authorized representative; obtain consent in compliance with French law.
2. Baseline Assessment
 - Collect demographics and clinical data (age, sex, weight, height, SAPS II, SOFA, reason for ICU admission, history).
 - Record renal data (CRRT indication and parameters, time since CRRT initiation).
 - Baseline hemodynamic measurements: CI, CVP, HR, MAP, PP, EVLW, PVPI, GEDVi, vasopressor dosage
 - Mechanical ventilation settings
3. Randomization
 - Determine challenge sequence (15 vs 30 minutes) using sealed envelopes.
4. Pre-test postural maneuver
 - Passive leg raise (supine) or Trendelenburg (prone).
 - Record hemodynamic parameters before and during maneuver.
5. Ultrafiltration Challenge
 - Remove 250 mL with UF over 15 or 30 minutes.
 - Monitor CI and hemodynamic parameters continuously.
 - Record parameters at the end of challenge.
6. Post-test Postural Maneuver (Reference)
 - Repeat maneuver (PLR or Trendelenburg).
 - Record hemodynamic parameters before and during maneuver.
7. Follow-up
 - Any hemodynamic instability episodes occurring over the following 8h

8. Second Ultrafiltration Challenge

- After a 24h wash-out period, repeat procedure with the alternate duration (30 or 15 minutes).
- Same sequence: pre-test maneuver → challenge → post-test maneuver.

9. Follow-up

- Monitor for 8 hours post-challenges.
- Record any hemodynamic instability.

Data Management

- Data recorded in a secure **electronic case report form (eCRF)**.

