STATISTICAL ANALYSIS

General Principles

- Analyses performed using R software (latest version available).
- Two-sided significance level set at 0.05.
- 95% confidence intervals reported.
- Analyses conducted on the intention-to-treat and per-protocol population (patients with at least one evaluable ultrafiltration challenge).

Primary Analysis

- The primary endpoint is the diagnostic performance of the ultrafiltration challenge (15- and 30-minute tests pooled).
- Performance assessed by calculating the area under the ROC curve (AUC) of cardiac index variation compared with the post-test postural maneuver.
- AUC values will be reported with 95% confidence intervals.

Secondary Analyses

1. Diagnostic performance of the 15-minute and 30-minute ultrafiltration challenge alone (ROC AUC).
2. Determination of the optimal threshold of cardiac index variation (Youden index) defining preload dependence, with sensitivity, specificity, PPV, and NPV.
3. Comparative diagnostic performance of ultrafiltration challenges (pooled and separate) versus the pre-test postural maneuver, compared using the

respective ROC AUCs of 15-minute and 30-minute challenges using DeLong's test.

4. Analysis of additional hemodynamic parameters (CVP, HR, MAP, PP, EVLW, PVPI, GEDVi) in absolute values and relative changes from baseline, correlated with cardiac index variation using Pearson or Spearman correlation.
5. Description of the incidence of hemodynamic instability within 8 hours post-test, expressed as proportions with 95% confidence intervals.

Handling of Missing Data

- Missing data will not be imputed.
- Analyses will be based on available data.
- The extent and reasons for missing data will be described.

Interim Analysis

No interim analysis is planned.

QUALITY ASSURANCE, ETHICS, AND DATA MANAGEMENT

Regulatory and Ethical Aspects

- The study will be conducted in compliance with the Declaration of Helsinki (2013 version) and the principles of Good Clinical Practice (ICH E6 R2).
- The protocol, patient information, and consent form have been submitted to and approved by the CPP Sud-Est VI (Comité de Protection des Personnes).
- The study has been declared to the CNIL (Commission Nationale de l'Informatique et des Libertés) in accordance with French law and the General Data Protection Regulation (GDPR, EU 2016/679).

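### The Youden cut-off is scored on the same 20 to 40 readings that chose it, so its Youden index, and its sensitivity when positives are few, will look clearly too favourable

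*Combined protocol and SAP*

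**What the plan says.** The Statistical Analysis section, Secondary Analyses item 2, plans "Determination of the optimal threshold of cardiac index variation (Youden index) defining preload dependence, with sensitivity, specificity, PPV, and NPV". The Summary, under Secondary Endpoints, adds an interval for the cut-off itself: "Optimal thresholds (and 95% CI) of cardiac index variation for each test, determined using the Youden index". Secondary objective 2 under Research Objectives asks for this "for each test (pooled and separate), with sensitivity, specificity, PPV, and NPV". That makes three searches: pooled, 15-minute and 30-minute.

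The Sample size section gives "20 patients planned" and "Total: 40 evaluable ultrafiltration challenges", hence 20 readings per duration. It adds: "The sample size was chosen pragmatically, consistent with the pilot/exploratory nature of the study".

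The plan fixes no cut-off for the ultrafiltration challenge in advance. It plans no split sample, cross-validation, optimism correction or external validation, and does not say that the accuracy figures will be presented as apparent. The primary endpoint is the pooled ROC AUC with a 95% CI.

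**The concern.** The Youden rule picks the cut-off at which sensitivity plus specificity is largest in the sample. Part of that maximum is chance. Quoting accuracy at that cut-off in the same readings keeps the chance part, so the sum is biased upwards, and more so the fewer the readings. The scarcer outcome class suffers most. Patients with recent preload dependence are excluded, so positives may well be the scarce class, and sensitivity is then the measure most inflated.

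The cut-off and its accuracy are what a bedside user or the next trial would take from this study; an AUC cannot be applied to one patient. The Summary's Expected Outcomes puts the current postural test's sensitivity below 80% for judging tolerance of fluid removal, suggests the challenge may be more sensitive, and foresees rapid uptake. Optimism alone could lift apparent sensitivity past that mark.

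**Working it through.** **Inputs from the documents.** 20 patients × 2 challenges = 40 readings, which reproduces the plan's total; 40 / 2 = 20 readings per duration. There is no power or precision figure to reproduce.

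**Assumptions, not in the documents.** True AUC 0.5 to 0.9. Positive post-test maneuver in 15 to 50% of readings. Equal-variance binormal marker. Within-patient correlation 0 or 0.5 in the pooled runs.

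**Method.** J = sensitivity + specificity − 1. In each simulated study, take the cut-off that maximises J, record accuracy in that sample (apparent), and compute the accuracy of the same cut-off in the population (true). Optimism = mean apparent − mean true. The tables below use 3,000 simulated studies per setting, dropping samples with fewer than 2 positives or 2 negatives.

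**All measures at AUC 0.80, apparent / true**

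| Readings, % positive | J | Sensitivity | Specificity | PPV | NPV |
|---|---|---|---|---|---|
| 40, 25% | 0.58 / 0.41 | 0.83 / 0.70 | 0.76 / 0.71 | 0.57 / 0.48 | 0.93 / 0.88 |
| 40, 50% | 0.56 / 0.42 | 0.78 / 0.71 | 0.77 / 0.71 | 0.79 / 0.72 | 0.79 / 0.73 |
| 20, 15% | 0.67 / 0.38 | 0.90 / 0.65 | 0.77 / 0.73 | 0.54 / 0.36 | 0.97 / 0.93 |
| 20, 25% | 0.63 / 0.39 | 0.86 / 0.68 | 0.77 / 0.72 | 0.62 / 0.49 | 0.94 / 0.88 |
| 20, 50% | 0.60 / 0.40 | 0.82 / 0.72 | 0.78 / 0.68 | 0.81 / 0.72 | 0.83 / 0.73 |

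The pooled rows use within-patient correlation 0.5. Setting it to 0 changes the optimism by at most about 0.01, so pairing is not the cause.

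**At 30% positive and AUC 0.80** (12 positive and 28 negative pooled; 6 and 14 per duration): J is 0.56 against 0.41 pooled, optimism 0.15, with sensitivity 0.80 against 0.68. Per duration J is 0.62 against 0.40, optimism 0.22, with sensitivity 0.84 against 0.66.

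**Optimism over AUC 0.7 to 0.9 and 15 to 50% positive**

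| Measure | Pooled | Per duration |
|---|---|---|
| J | about 0.12 to 0.23 | about 0.16 to 0.31 |
| Sensitivity, points | about 6 to 19 | about 8 to 26 |
| Specificity, points | about 3 to 8 | about 3 to 11 |

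These limits move by 0.01 or so with the handling of ties and of the number of positives. Pooled PPV is inflated by about 5 to 11 points and NPV by 3 to 8.

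**Role of sample size.** At AUC 0.80, 25% positive and independent readings, optimism in J is 0.17 with 40 readings, 0.07 with 200 and 0.04 with 400.

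**Check of remedies, mean J with 40 readings, correlation 0.5** (300 simulated studies each)

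| AUC, % positive | Apparent | Bootstrap-corrected | Leave-one-patient-out | True |
|---|---|---|---|---|
| 0.7, 25% | 0.44 | 0.32 | 0.24 | 0.25 |
| 0.8, 25% | 0.59 | 0.48 | 0.41 | 0.41 |
| 0.9, 25% | 0.72 | 0.63 | 0.56 | 0.59 |
| 0.8, 50% | 0.56 | 0.47 | 0.41 | 0.42 |

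In the second row the bootstrap removes (0.585 − 0.477) / (0.585 − 0.410) = 0.108 / 0.175 = 62% of the optimism. With 20 readings of the 6-and-14 kind and AUC 0.5, J is 0.28 apparent, 0.13 after bootstrap correction, 0.04 by leave-one-patient-out and 0 in truth.

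**The case against.** This is a secondary analysis in a declared pilot. The primary measure is an AUC with a 95% CI, AUCs are also reported per duration, and none of these needs a cut-off on the challenge. The Summary plans a CI for the threshold, and 95% CIs are promised generally. Sampling error also exceeds the bias: 10 of 12 positives detected has an exact 95% CI of about 0.52 to 0.98, and 5 of 6 about 0.36 to 1.00, so the true values of 0.68 and 0.66 lie well inside.

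Most of this stands and limits the weight of the point. It does not remove the bias. A CI for the threshold shows that the cut-off is unstable, while ordinary intervals for sensitivity and specificity at a selected cut-off are centred on inflated values. Pilot status is a reason to label the figures as apparent, which the plan does not do.

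A reader might infer that all four accuracy measures will be markedly too good. The planned numbers do not support that across the board: pooled specificity gains only about 3 to 8 points, and at 50% positive the optimism is spread about evenly over the measures. A reader might also infer that a worthless test would pass as a good one. At AUC 0.5 the apparent J is indeed 0.18 to 0.27 pooled and 0.24 to 0.32 per duration. At 30% positive, however, that is roughly 0.66 sensitivity with 0.54 specificity pooled, or 0.72 with 0.55 per duration. Such figures would not look like a good test, and the plan reports an AUC with its interval beside them.

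**Conclusion.** The point holds for the secondary threshold analysis. Followed as written, the plan yields a Youden index, and a sensitivity when positives are few, that are clearly too favourable, most of all in the 20-reading analyses. Specificity and NPV are inflated less. So is PPV when the readings are pooled, but with 20 readings and 15% positive its optimism at AUC 0.80 is about 19 points (0.544 − 0.356).

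The size rests on assumed AUC and prevalence and on a binormal marker, but no setting examined removed the optimism. The comparison with the below-80% figure is indicative only: the protocol's background section separately credits the postural test with sensitivity and specificity above 85% for diagnosing preload dependence.

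The documents give no ground for extending the point to the primary AUC. It is a change that should be made, not a flaw in the primary analysis.

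**What to change.** In Secondary Analyses item 2, for the pooled, 15-minute and 30-minute tests:

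- Keep the uncorrected sensitivity, specificity, PPV and NPV, labelled *apparent*.
- Beside them, report leave-one-patient-out cross-validated values. Redo the whole cut-off search each time without that patient's readings (both readings in the pooled analysis), then classify the patient left out.
- Take the threshold's 95% CI, which the Summary promises without naming a method, from a bootstrap that resamples patients.
- If bootstrap optimism subtraction is also shown, state that it removes only part of the optimism at this sample size.
- State that the threshold needs external validation before use.

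The cost is a few lines of SAP text and a short resampling program, with no new data or patients. The price is accuracy figures that are less favourable and somewhat more variable.

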- Comparative diagnostic performance of ultrafiltration tests (pooled and separate) versus pre-test postural maneuver, and between tests (15 vs. 30 minutes).
- ROC AUC values compared using DeLong's method.
- Hemodynamic variables measured by cardiac output monitoring (CVP, HR, MAP, pulse pressure, EVLW, PVPI, GEDVi), analyzed as absolute values and changes from baseline, correlated with cardiac index variation.
- Incidence of hemodynamic instability (tachycardia, hypotension, decreased cardiac index, mottling) within 8 hours after the ultrafiltration test.

Target Population

Adult ICU patients (under mechanical ventilation and sedation) with acute kidney injury (KDIGO stage 3) requiring continuous renal replacement therapy initiated within the past 14 days.

Sample Size

N = 20 evaluable patients, each undergoing 2 tests → total of 40 rapid ultrafiltration challenges.

Study Duration

- Inclusion period: 18 months
- Maximum participation per patient: 72 hours
- Total study duration: 18 months + 3 days

Expected Outcomes

The current reference dynamic test (passive leg raise or Trendelenburg) remains imperfect in assessing tolerance to fluid removal during CRRT, with sensitivity <80%. The UF challenge may prove more sensitive, particularly in patients at the borderline between the ascending and plateau phases of the Frank-Starling curve. This simple, dynamic, low-cost test could help clinicians individualize ultrafiltration prescriptions, avoid deleterious hypotension, and rapidly integrate into clinical practice. Currently, no specific dynamic test exists to evaluate the safety and efficacy of fluid removal in this population.

GENERAL INFORMATION

Title: Diagnostic performance of a rapid ultrafiltration test to assess preload dependence in critically ill patients treated with continuous renal replacement therapy.

Project Identifiers and Update History

- Sponsor Code: 69HCL21_1250
- ClinicalTrials.gov registration number: NCT05214729
- CPP Sud-Est VI favorable opinion date: XX/XX/XXXX

Version History

Version	Date	Reason for Update
1	02/11/2021	Initial draft
2	16/03/2022	Comments from CPP

Sponsor

Identity: Hospices Civils de Lyon

[name]

[name] [name]

Signature of the protocol on behalf of the Sponsor:

[name], Director of Health Research

Hospices Civils de Lyon, Health Research Directorate,

Administrative Headquarters,

[name],

[name],

[name]

[contact]

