- Each patient undergoes 2 ultrafiltration challenges (15- and 30-minute, in randomized order)
- Total: 40 evaluable challenges

Randomization

- Randomized order determined by sealed envelope method
- Each patient serves as their own control

Blinding

- Not feasible given the study design

Co-interventions

Recommendation for not changing any of the following parameters, prescription or settings during the trial's interventions:

- Sedation
- Mechanical ventilation
- Vasopressor and inotrope support
- Fluid bolus therapy or transfusion

Study Procedures

1. Baseline data collection (demographics, clinical scores, renal data, hemodynamics)

2. Calibration of the monitoring device and pre-test postural maneuver (PLR or Trendelenburg) during 1 minute with collection of the relative change in continuous cardiac index
3. Ultrafiltration challenge: 250 mL over 15 or 30 minutes (randomized), by setting a UF flow of 1000 ml/h or 500 ml/h, respectively
4. Re-calibration of the monitoring device and post-test postural maneuver (reference standard, PLR or Trendelenburg) during 1 minute with collection of the relative change in continuous cardiac index
5. Repeat sequence for second challenge after a wash-out period of 24h (cross-over design)
6. Follow-up: monitoring for 8 hours post-test for instability

Data Collected

- Demographics: age, sex, weight, height
- Clinical: history, reason for ICU admission, severity scores (SAPS II, SOFA)
- Renal: CRRT indication and parameters
- Hemodynamics: CI, CVP, HR, MAP, PP, EVLW, PVPI, GEDVi (before/after each step), vasopressor dosage
- Ventilatory settings: VT, PEEP, FiO₂, arterial blood gas results
- Results of the pre and post-test postural maneuvers
- Any severe and non-severe adverse events

ENDPOINTS / EVALUATION CRITERIA

Primary Endpoint

The diagnostic performance of the rapid ultrafiltration challenge (pooled 15- and 30-minute tests).

- Performance assessed by the area under the ROC curve (AUC) of cardiac index variation.
- Reference: continuous cardiac index relative variation induced by the post-test postural maneuver performed after the challenge.

Secondary Endpoints

1. Respective diagnostic performance of the 15-minute and 30-minute challenges (ROC AUC).
2. Determination of the optimal threshold of cardiac index variation (Youden index) with sensitivity, specificity, PPV, and NPV.
3. Comparative performance of challenges (pooled and separate) versus the pre-test postural maneuver.

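### Most of the plan measures the change in central venous pressure as a percentage. The mmHg difference is the more stable measure, and the wording should be reconciled with the summary endpoint.

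*Combined protocol and SAP*

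**What the plan says.** The plan describes how CVP is analysed in five places, and they do not agree fully.

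- **Statistical Analysis, Secondary Analyses item 4:** seven variables, CVP first, are analysed "in absolute values and relative changes from baseline", and these are correlated with cardiac index variation "using Pearson or Spearman correlation".
- **Research Objectives, Secondary Objectives item 5:** the effect of the challenges on "other hemodynamic parameters (absolute values and relative changes from baseline): central venous pressure (CVP" and the six others. The Summary's Secondary Objectives say the same in substance.
- **Endpoints, Secondary Endpoints item 5:** "absolute values and relative changes, correlated with cardiac index variation".
- **Summary, Secondary Endpoints:** "analyzed as absolute values and changes from baseline, correlated with cardiac index variation". The word relative is absent here.

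The list under Data Collected includes "Hemodynamics: CI, CVP, HR, MAP, PP, EVLW, PVPI, GEDVi (before/after each step), vasopressor dosage", so raw CVP is available on both sides of each challenge. No passage says what to do when the baseline CVP is at or near zero. Missing values are not imputed, and analyses use available data. No rule is given for choosing between the two correlation methods.

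**The concern.** On the plain reading, absolute values are levels before and after, not differences. The effect of a challenge, and its correlation with the cardiac index response, needs a change for each challenge. In four of the five places the only change named is the percentage.

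A percentage needs a meaningful zero and a denominator well away from it. CVP has neither: it is a few mmHg above a chosen reference level. The same 1 mmHg fall becomes a very different percentage depending on where the patient started, and there is no percentage when the reading is 0. A mean percentage, or a Pearson correlation based on it, can then reflect which patients started low more than what ultrafiltration did. At stake is the reading of one of the seven variables in secondary objective 5.

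**Working it through.** **The plan's own figure.** 20 patients × 2 challenges = 40 challenges, as stated. The plan gives no power, effect size or CVP distribution, so there is no power figure to reproduce.

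**Step 1: the ratio itself.** Percentage change = 100 × (end − start) / start. For a fall of 1 mmHg:

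- start 12: −1/12 = −8%
- start 2: −1/2 = −50%
- start 0: undefined

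**Step 2: dependence on the zero level.** Assume baseline mean 10, SD 3 mmHg, a true mean change of −1 (SD 1), and reading error SD 0.7. Moving only the zero level by −3, 0 and +3 mmHg leaves the mean mmHg change at about −1.0. The mean percentage change goes from −15.6% to −10.5% to −7.8%. No assumption about cardiac index enters here.

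**Step 3: how few readings carry the variance.** All inputs are assumptions:

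- true baseline mean 8, SD 4 mmHg, floored at 0
- true change mean −1, SD 1
- reading error SD 0.7 at each time point, with readings rounded to whole mmHg

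In 400,000 simulated challenges, readings of 3 mmHg or less were 11% of the defined values but gave 56% of the variance of percentage change. That share was 61% at baseline mean 6 (SD 3), 39% at mean 10 (SD 4) and 24% at mean 12 (SD 4). Undefined values were 2.8% of challenges at mean 8, and 0.2% to 3.3% across this range.

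**Step 4: power of the correlation.** Same inputs, with the true mmHg change correlated 0.7 with cardiac index change; two-sided 0.05; challenges treated as independent; zero baselines dropped from the percentage. Each cell uses 3,000 simulated studies (Monte Carlo error below 1 point).

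| Rows | Method | mmHg change | Percentage change |
|---|---|---|---|
| 20 | Pearson | 55.3% | 39.8% |
| 20 | Spearman | 51.4% | 46.5% |
| 40 | Pearson | 86.5% | 69.1% |
| 40 | Spearman | 81.9% | 78.2% |

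Hand check for Pearson with 40 rows, where power ≈ Φ(atanh(r) × √37 − 1.96):

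- mmHg, mean simulated r 0.457: 0.4936 × 6.083 − 1.96 = 1.04, so 85%
- percentage, mean simulated r 0.382: 0.4024 × 6.083 − 1.96 = 0.49, so 69%

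Across baseline means of 6, 8 and 12, the Spearman loss with 40 rows was 2.8 to 3.7 points. With other assumed inputs (change −1.5, SD 1.5; true correlation 0.4 to 0.5; rounding but no separate reading error) the losses were about 14 to 22 points for Pearson and 8 to 10 for Spearman.

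**Step 5: if the true link is proportional.** Let the true percentage change (mean −12.5%, SD 12.5%) be what correlates 0.7 with cardiac index change. With reading error 0.7 and 40 rows, Pearson power is 82% (mmHg) against 62% (percentage) at baseline mean 8, and 96% against 92% at mean 12. Without reading error the order reverses. In the −1.5 mmHg setting with true correlation 0.4, it is 54–65% (mmHg) against 67–72% (percentage).

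**The case against.** Four points can fairly be made against this.

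1. **The percentage is not the only change measure in the document.** A reader might infer that CVP change would be read solely as a percentage. The Summary endpoint's unqualified changes from baseline can include a mmHg difference, and levels before and after are also analysed. This stands: the fault is an inconsistency plus an inferior measure named in the analysis section, not a complete omission.
2. **Spearman is allowed.** A reader might infer that a few low readings must drive the correlation. The plan says "using Pearson or Spearman correlation", and ranking limits the pull of extreme percentages. This largely stands for power. It does not make the mean percentage stable or define a value at baseline 0, and nothing commits the analysts to Spearman.
3. **The loss of power is not a fact about this trial.** Every CVP input is assumed, and the main scenario places the true link on the mmHg scale, which favours the mmHg measure. This stands. With reading error included, Pearson still favoured mmHg under a proportional link, but without reading error it did not.
4. **Dropping the percentage has a price.** If proportional change is the relevant scale, removing a prespecified measure loses information. This also stands, so the percentage may remain as description.

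Materiality is low in any case. This is one variable in a secondary analysis of a pilot study whose sample size was chosen pragmatically, and the primary AUC is untouched.

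**Conclusion.** The point holds as a minor one. The Summary objectives, objective 5, endpoint 5 and Secondary Analyses item 4 name percentage change for a variable to which percentages are poorly suited, and the Summary endpoint is worded differently. The instability at low baselines and the undefined value at 0 follow from the formula and need no assumption. Their size does: under the inputs above, with 40 challenges treated as independent, Pearson power is about 87% for mmHg change and 69% for percentage change, while the Spearman loss is about 2 to 4 points. Pairing of two challenges within a patient is ignored, so power for either measure may be lower. The documents do not support the stronger reading that the CVP result will be driven by a few readings, or that a real effect will be missed.

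**What to change.** In objective 5, endpoint 5 and Secondary Analyses item 4 (and the matching Summary objective), reconcile the wording with the Summary endpoint. State that CVP change, including its correlation with cardiac index change, is analysed as the mmHg difference: the value at the end of the challenge minus the value just before the same challenge. Any percentage change kept for CVP should be descriptive only, with a note on how zero or near-zero baselines are handled. Naming in advance which correlation method applies would close the remaining gap.

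The cost is a phrase in each place. The CVP values needed are already collected before and after each step, and no other analysis changes.
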